### **Mycophenolate Mofetil (Cellcept®)**

Cellcept® will be given at a dose of between 750 to 1000 mg PO twice daily. The first dose will be given on Day 0 (day of kidney transplant surgery). This medication will be given in an open label fashion. There will not be any change in the dose of Cellcept® at the time of randomization unless indicated by medical reasons (i.e. Neutropenia, GI side effects.)

### **Tacrolimus (Prograf®)**

Tacrolimus will be given 1-2 mg PO twice daily, beginning Day 1 (post-operative Day 1). The dose will be modified to achieve 12 hour trough concentrations of 6-10 ng/ml. This medication will be given in an open label fashion.

## **Alemtuzumab (Campath®)**

The first dose of Campath® will be 30 mg given IV, and administered intra-operatively during renal transplantation. This medication will be given in an open label fashion and will only be administered while the patient is in the hospital in the immediate post-transplant period.

## **Corticosteroids (methylprednisolone)**

Time:	Dose
Preop (Intraop/Day 0)	500 mg
POD#1 (Day1)	250 mg
POD#2 (Day2)	125mg
POD#3(Day 3)	0 mg

## **Statistical Analysis**

Once the 2 groups of renal transplant patients are identified, two sample t tests will be used to compare differences in continuous variables between groups; chi square tests will be used to compare differences in discrete variables. Multivariable logistic regression analysis will be also performed to identify the combination of clinical variable that are significantly associated with the development of acute rejection and renal allograft function after conversion from tacrolimus →sirolimus.

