### **Research Objective**

The aim of the present study is to prospectively investigate the impact of CI conversion (tacrolimus→sirolimus) between 6 and 24 months post-transplant on the incidence of acute cellular rejection, renal allograft function and lymphocytes function.

Primary aim of the study is:

to investigate the impact of CI conversion (tacrolimus→sirolimus) on the incidence of acute cellular rejection.

Secondary aims of the study are:

- i) evaluate whether CI conversion (tacrolimus→sirolimus) contributes positively or negatively on the renal allograft function calculated with e-GFR and proteinuria;
- ii) patient and graft survival ;
- iii) evaluate if CI conversion impacts on lipid profile, incidence of hypertension, malignancies, and opportunistic infections and post-transplant DM;
- iv) evaluate possible modifications of lymphocytes function before and after conversion (tacrolimus→sirolimus)
- v) assess tubular toxicity by evaluating urinary biomarkers

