### **Data Collection**

The following data will be collected at the time of randomization:

Recipient demographics- such as age at transplantation, sex and race.

Clinical history- Causes of end-stage renal disease, past medical history

Transplant related information- donor age, cadaveric versus living kidney transplant, histocompatibility and cross match data, viral serology, history of acute rejection and delayed graft function, use of induction therapy and immunosuppressants, use of ACEI and/or ARB, level of renal allograft function- estimated GFR (e-GFR(12) using MDRD formula, proteinuria.

Peripheral blood leukocytes will be obtained from renal transplant recipients for baseline (prior to randomization) lymphocytes functional activity and characterization of lymphocytes subpopulations by flow cytometry analysis.

Peripheral donor leukocytes (from living donor patients) will also be obtained at the time of randomization. These donor leukocytes will be used as stimulator cells to study the functional activity of the recipient's lymphocytes function.

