### **Post randomization**

The recipients assigned to continue with tacrolimus and MMF will be routinely followed at our outpatient Transplant center with monthly labs. In addition to the baseline pre-randomization labs, at 6, 12 and 24 months post randomization, peripheral blood leukocytes will be obtained to study lymphocytes functional activity and to characterize lymphocytes subpopulations by flow cytometry analysis.

Post randomization, the recipients assigned to switch from tacrolimus to sirolimus and continue with MMF will be routinely followed at our Transplant center with monthly labs. Furthermore, during the period of conversion from tacrolimus to sirolimus, weekly labs will be obtained to monitor renal function and bone marrow function. In addition to the baseline pre-randomization labs, and labs collected at 6, 12, 24, 36, and 48 months post randomization, peripheral blood leukocytes will be obtained to study lymphocytes functional activity to characterize lymphocytes subpopulations by flow cytometry analysis and urine will be collected to assess tubular toxicity by evaluating urinary biomarkers.

Both groups of patients will be followed for 4 years post-randomization. In addition to monitoring renal allograft function, we will evaluate the incidence of acute rejection, patient and graft survival, the impact of CI conversion on the lipid profile, the incidence of hypertension, malignancies, opportunistic infections and post-transplant DM.

Furthermore, with the peripheral leukocytes obtained at baseline prior to randomization and at 6, 12, 24, 36, and 48 months post-randomization we will investigate possible modifications of lymphocytes function and of the lymphocytes subpopulations that might have occurred as a consequence of the switch from tacrolimus to sirolimus.

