### **Exclusion Criteria**

- 1) Subjects with ESRD secondary to primary FSGS (focal segmental glomerulonephritis).
- 2) Inability to comply with study procedures
- 3) Inability to sign the informed consent
- 4) Subjects with a significant or active infection
- 5) Subjects who are pregnant or nursing females
- 6) Subjects with a history of severe hyperlipidemia not controlled with statins, patients with at total cholesterol of  $> 400$  mg/dl
- 7) Subjects with a platelet count  $< 100,000\text{mm}^3$  WBC  $< 2,000\text{mm}^3$
- 8) Subjects with severe proteinuria at the time of randomization ( $> 2\text{gm/day}$ )
- 9) Subjects with more than 2 episodes of acute cellular rejection post transplantation will be excluded from this study
- 10) An estimated GFR  $< 40$  cc/min (This will be calculated by MDRD or by Cockcroft-Gault formulas, which are both are commonly used formulas for estimated GFR.)
- 11) A history of malignancy during the post-transplant period (other than treated basal cell cancer and/or squamous cell cancer)
- 12) Subjects, who, due to the existence of a surgical, medical or psychiatric condition, other than the current transplant, which in the opinion of the investigator, precludes enrollment into this trial
- 13) A history of ACR during the most recent previous 3 months prior to randomization

\*\*Other: prior to approaching any individual who has undergone desensitization procedures prior to transplant, we must first check with Dr. [name]

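### Renal function (secondary aim i): the plan offers only a t-test with no baseline adjustment, names no visit or form of comparison, and names logistic regression with no binary renal outcome

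*Combined protocol and SAP*

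**What the plan says.** The document is a combined protocol and SAP, and the plan for analysis is the short Statistical Analysis section.

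- **Aim.** Under Research Objective, secondary aim i asks whether conversion "contributes positively or negatively on the renal allograft function calculated with e-GFR and proteinuria".
- **Baseline.** Data Collection lists, at the time of randomisation, "level of renal allograft function- estimated GFR" by the MDRD formula, and proteinuria.
- **Comparison of arms.** Statistical Analysis states that "two sample t tests will be used to compare differences in continuous variables between groups", with chi-square tests for discrete variables.
- **Regression.** The same section adds multivariable logistic regression to find clinical variables "significantly associated with the development of acute rejection and renal allograft function after conversion from" tacrolimus to sirolimus.
- **Follow-up.** Post randomization states "Both groups of patients will be followed for 4 years post-randomization" and gives both arms monthly labs. The tacrolimus paragraph says "at 6, 12 and 24 months post randomization, peripheral blood leukocytes will be obtained"; the sirolimus paragraph refers to "labs collected at 6, 12, 24, 36, and 48 months post randomization". These time points are attached to leukocyte samples and, in the sirolimus paragraph, urinary biomarkers. None is designated for comparing eGFR or proteinuria.
- **Renal thresholds.** The only numeric ones are in Exclusion Criteria: estimated GFR below 40 cc/min and proteinuria above 2 gm/day. Both decide eligibility.

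**The concern.** Nephrotoxicity of calcineurin inhibitors is the rationale set out in Background, so the renal comparison is likely to be read closely even though it is secondary. Three things are unsettled.

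1. **Precision.** Baseline eGFR will be in the database and can be expected to predict later eGFR. The plan names no analysis that adjusts for it.
2. **Visit and form.** With four years of labs and open-label treatment, a visit and a form (value or change) chosen later could be chosen with results in view.
3. **Model.** Logistic regression needs a binary outcome. For renal function there is none, so the model cannot be fitted until someone picks a cut-off, possibly after seeing the data.

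**Working it through.** **No plan figure to reproduce.** The documents give no SD, effect size, alpha or power for eGFR, so everything numerical below is illustrative.

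**Inputs from the documents.** 275 randomised at 2:1 (Randomization), that is about 92 and 183.

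**Assumed inputs.** SD 18 mL/min (range 15 to 20); correlation r between baseline and follow-up eGFR 0.5 to 0.7; two-sided alpha 0.05; 80% power; no dropout.

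**Step 1: detectable difference.** For a t-test on follow-up values:

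(1.960 + 0.842) × SD × √(1/92 + 1/183) = 2.802 × 18 × 0.1278 = 6.45 mL/min.

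A t-test on change multiplies this by √(2(1 − r)); ANCOVA on baseline multiplies it by √(1 − r²).

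| r | t-test, follow-up value | t-test, change | ANCOVA |
|---|---|---|---|
| 0.5 | 6.45 | 6.45 | 5.58 |
| 0.6 | 6.45 | 5.76 | 5.16 |
| 0.7 | 6.45 | 4.99 | 4.60 |

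The gain from ANCOVA is 0.9 to 1.8 mL/min over the follow-up t-test, and 0.9 falling to 0.4 over the change t-test. Over SD 15 to 20, the follow-up t-test detects 5.37 to 7.16 and ANCOVA 3.84 to 6.20. With 20% missing in each arm (73.6 versus 146.4) and SD 18, the figures are 7.21, 7.21 to 5.58, and 6.24 to 5.15.

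**Step 2: the same gain in subjects.** To match ANCOVA with 275 subjects:

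- a follow-up t-test needs 275/(1 − r²) = 367 (r = 0.5) to 539 (r = 0.7);
- a change t-test needs 275/((1 + r)/2) = 367 to 324.

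**Step 3: the open visit.** Mean differences were simulated with no true effect, counting how often at least one test has |z| > 1.96. Two correlation patterns were used: equal correlation r among all visits including baseline, and follow-up visits correlated 0.85 per step apart with correlation r to baseline.

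| Tests available | Chance of at least one p < 0.05 |
|---|---|
| 5 visits, follow-up value only | about 13.5% to 18% |
| 5 visits, value and change (10 tests) | about 24% to 31% |
| 3 visits listed for both arms, value and change (6 tests) | about 17% to 22% |

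**Step 4: the logistic model.** This needs no assumption. eGFR is continuous, no section defines a binary renal outcome, and the two numeric limits are entry criteria. The model cannot be run as named.

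**The case against.** The strongest reply is that the plan does not rule out the use of baseline. A t-test on change would use it, and then ANCOVA gains only 0.9 to 0.4 mL/min (about 0.2 at r = 0.8: 4.08 versus 3.87). This stands, and it limits the claim. A reader might infer that the plan discards baseline, or that 539 subjects is the cost; the documents support neither, because they do not say which form is meant. It remains true that no form is chosen and that ANCOVA is at least as precise as either.

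Other stronger readings also fail:

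- **That the t-test is invalid or biased.** It is valid as randomised.
- **That the plan carries a 24% to 31% error rate.** That figure requires all ten tests to be run and any one to be claimed. The five visits are also sampling times for leukocytes and biomarkers, not stated eGFR analysis visits.
- **That the eGFR formula is contradictory.** Data Collection names MDRD for renal function. The statement "This will be calculated by MDRD or by Cockcroft-Gault formulas" concerns eligibility only, and no section offers Cockcroft-Gault for the outcome. Confirming MDRD at follow-up is enough.
- **That the multivariable model already supplies the adjustment.** It is described as a search for associated variables after conversion, not as an adjusted comparison of arms.

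Two further cautions are fair. The t-test sentence does not name eGFR or proteinuria; the link is an inference, sound for eGFR. For proteinuria the documents give neither a measurement scale for the outcome nor a follow-up schedule, so it cannot be assumed to suit the same model.

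**Conclusion.** The point holds as an improvement the sponsor should make; it does not threaten the validity of the trial. Two findings rest on the text alone: no visit or form is designated for the renal comparison, and logistic regression is named for an outcome with no binary definition. The third, unused precision, is real but its size depends on the assumed SD and correlation and on which t-test was intended: the detectable difference could fall from 6.45 to between 5.58 and 4.60 mL/min against a follow-up t-test, and by much less against a change t-test when r is high. The selection risk is best quoted as about 13.5% to 18% for follow-up values over five visits, with 24% to 31% as the worst case.

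**What to change.** In Statistical Analysis, add wording such as:

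> eGFR (MDRD at baseline and follow-up) will be compared between arms as randomised, by ANCOVA with terms for arm and baseline eGFR, at one named visit (for example 24 months post randomisation), with other visits supportive. The adjusted difference will be reported with its 95% CI.

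The 24-month visit is only an example: it is the last one listed in both arms' paragraphs and is a planned biopsy time. In addition:

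- Use a linear model for predictors of eGFR and keep logistic regression for acute rejection. If a binary renal outcome is wanted, define its cut-off now.
- Analyse proteinuria with baseline adjustment in the same way, on the log scale only if it is measured quantitatively at baseline and follow-up. State its scale and follow-up schedule.

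**Cost.** For eGFR, SAP wording and minor analysis work: baseline eGFR is already collected and monthly labs are planned in both arms. For proteinuria, the cost depends on whether follow-up measurement is already planned, which the documents do not state.

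**Limit.** Adjustment does not cure eGFR or proteinuria that is missing after withdrawal (Early Withdrawal of Subjects commits only to attempting at least survival data) or affected by the switch back to tacrolimus under Stopping Rules, where proteinuria is itself a trigger. The SAP should say separately how such values are handled.

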### **Randomization**

For this research study, between 6 and 24 months post-transplant we plan to prospectively randomize 2:1 renal transplant patients to either:

- Continue with tacrolimus and MMF or
- Substitute tacrolimus with sirolimus and continue MMF

A total of 400 pts. are expected to be screened for the randomization and we expect to be able to randomize 275 renal transplant patients into this protocol.

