## **Biopsy**

Chronic nephrotoxicity from calcineurin-inhibitors (CI) has been implicated as a principal cause of post-transplant renal dysfunction and it is characterized by an irreversible and progressive tubular atrophy, interstitial fibrosis, and focal hyalinosis of small renal arteries and arterioles. Furthermore, chronic nephrotoxicity from CI has been documented in all non-renal transplants and the chronic renal failure secondary to the use of CI has been associated with an increase in mortality by a factor of more than four.

The present proposal is to identify those subjects already participating in this study who are willing to undergo a kidney biopsy with the aim of evaluating renal allograft pathology and renal allograft tissue gene expression profiles of the two groups of patients maintained on Tacrolimus/ MMF or switched to SRL/MMF. Performing kidney biopsies on the subjects who consent for the procedure will allow us to address the effect of immunosuppressive modifications on renal allograft pathology at 24 months post randomization. We also plan to obtain renal allograft biopsies at 12 months post-transplant (standard of care) in order to establish a baseline parameter for to compare the 24 month sample. An additional biopsy at 48 months will allow us to examine long term results of graft function. We also plan to obtain renal allograft biopsies to be stored in RNA later to further extend our knowledge on the effect of CI free immunosuppression on gene expression profiles.

Obtaining renal allograft tissue samples at 24 and 48 months post randomization can have potential important ramifications to help explain the mechanisms of fibrosis and tubular atrophy typically associated with CI and the role of CI elimination with the substitution of SRL. All data will then be analyzed comparing gene expression profiles of peripheral blood (Paxgene tubes are routinely collected at the different time points as part of the original study). Based on power analysis, we will perform 24 and 48 months post randomization biopsies in 70% of the total subjects enrolled in the study (approximately 46 subjects from the tacrolimus/MMF group and approximately 93 subjects from the sirolimus/MMF group).

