## **Safety and Adverse Events**

For the purpose of this clinical trial, the National Cancer Institute Common Terminology Criteria for Adverse Events v3.0 (CTCAE), dated December 12, 2003 will be used to grade all adverse events.

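### Ordered outcomes (CTCAE grade, and biopsy pathology if it is graded) get only an unordered chi-square, which is valid but inefficient for a one-directional shift

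*Combined protocol and SAP*

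**What the plan says.** The Statistical Analysis section is one short paragraph. For continuous outcomes, "two sample t tests will be used to compare differences in continuous variables between groups". For the rest, "chi square tests will be used to compare differences in discrete variables". It adds a multivariable logistic regression for factors associated with rejection and graft function. It gives no separate rule for ordered categories.

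Two other sections bear on this:

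- **Safety and Adverse Events** says that CTCAE v3.0 "will be used to grade all adverse events". Primary Safety Endpoints rests the safety assessment on the adverse events and serious adverse events observed.
- **Biopsy** aims at "evaluating renal allograft pathology and renal allograft tissue gene expression profiles of the two groups of patients" and hopes to "help explain the mechanisms of fibrosis and tubular atrophy typically associated with CI". It gives no score, grade or scale for pathology. On sample size: "Based on power analysis, we will perform 24 and 48 months post randomization biopsies in 70% of the total subjects enrolled in the study", given as "approximately 46 subjects from the tacrolimus/MMF group and approximately 93 subjects from the sirolimus/MMF group".

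**The concern.** A Pearson chi-square on a table of two arms by four ordered grades treats the grades as interchangeable labels. It spreads its sensitivity over 3 degrees of freedom, whereas the natural question has one direction: does one arm tend to have lower grades than the other? It also yields a p-value without an estimate of how far the arms differ.

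The Biopsy section asks about just such a direction, namely whether replacing the calcineurin inhibitor changes chronic damage. The biopsies are invasive and taken only from subjects who consent. If pathology is read in grades, a test that uses the order gets more from the same tissue. The same holds for any comparison of adverse-event severity between arms.

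**Working it through.** **1. Sample sizes.** The Biopsy section gives 46 + 93 = 139 subjects and calls this 70% of those enrolled. Randomization says "we expect to be able to randomize 275 renal transplant patients into this protocol".

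- 0.70 × 275 = 192.5. Split 1:2, this is 192.5/3 = 64.2 and 2 × 64.2 = 128.3, or about 64 versus 128.
- 139/275 = 50.5%, and 139/0.70 = 198.6.

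So 139 does not reproduce from 70% of 275; it fits 70% of about 200. The power analysis cannot be reproduced either, because no endpoint, effect, alpha, power or test is given. Both sample sizes are carried forward.

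**2. Assumptions, none from the documents.** Two-sided 5% level; four ordered grades; a common odds ratio (OR) towards lower grades in the sirolimus arm. Each cumulative odds is multiplied by the OR. For a control distribution of 25/40/25/10% and OR 2:

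- cumulative 25%: odds 0.333 → 0.667, so 40.0%
- cumulative 65%: odds 1.857 → 3.714, so 78.8%
- cumulative 90%: odds 9 → 18, so 94.7%

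The sirolimus arm is then 40.0/38.8/15.9/5.3%.

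**3. Simulated power, chi-square (3 df) versus tie-corrected Wilcoxon.** With control distributions 25/40/25/10% and 40/35/18/7%:

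- 46 versus 93, OR 2: 39–40% versus 53–55%
- 46 versus 93, OR 2.5: 61–64% versus 76–78%
- 64 versus 128, OR 2 to 2.5: about 53–78% versus 68–90%

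Three other control distributions, with 20,000 trials per cell, check the sensitivity to that choice (chi-square / Wilcoxon, %):

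| Control grades (%) | Arms | OR 1 | OR 1.5 | OR 2 | OR 2.5 | OR 3 |
|---|---|---|---|---|---|---|
| 20/40/30/10 | 46/93 | 4.7 / 5.0 | 15.7 / 23.5 | 39.6 / 54.9 | 63.6 / 78.5 | 80.6 / 90.8 |
| 40/35/20/5 | 46/93 | 4.5 / 4.8 | 16.6 / 22.3 | 39.6 / 53.2 | 62.0 / 75.3 | 77.6 / 88.3 |
| 25/25/25/25 | 46/93 | 4.9 / 5.1 | 16.1 / 23.8 | 40.3 / 56.2 | 65.5 / 79.7 | 81.7 / 91.8 |
| 20/40/30/10 | 64/128 | 5.3 / 5.1 | 20.1 / 30.1 | 52.9 / 69.2 | 79.2 / 90.1 | 91.8 / 97.1 |
| 40/35/20/5 | 64/128 | 4.7 / 4.7 | 20.3 / 29.5 | 52.8 / 67.6 | 77.2 / 88.3 | 90.2 / 96.0 |
| 25/25/25/25 | 64/128 | 4.9 / 5.1 | 20.9 / 31.3 | 54.3 / 71.0 | 80.1 / 90.5 | 92.9 / 97.5 |

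The OR 1 column is the type I error, close to 5% for both tests. The power ranges agree with the first pair of distributions to within about two points.

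**4. Analytic cross-check.** For 80% power at 5%, a 1-df test needs a noncentrality of 7.85 and a 3-df test needs 10.90. The ratio is 10.90/7.85 = 1.39, or about 39% more subjects. At a noncentrality of 7.85 the 3-df test has 64% power.

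**5. CTCAE.** Assume worst grade per subject in five levels (10/30/35/20/5% in the control arm) and all 275 subjects split 1:2, about 92 versus 183. OR 1.5 gives 25% versus 41%; OR 2 gives 66% versus 85%.

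**6. The reverse case.** Take 25/25/25/25% versus 15/35/35/15% at 46 versus 93, a difference with no overall direction. Chi-square has about 46% power and Wilcoxon about 7%.

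**The case against.** The best reply is that the plan never says biopsy pathology is graded. If fibrosis were measured on a continuous scale, the t test would apply. If it were recorded as present or absent, chi-square and Wilcoxon would be essentially the same test. Nor does the plan announce a between-arm test of CTCAE grade; worst grade per subject is a summary proposed here. All of this stands, so the biopsy part of the point is conditional.

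It also stands that the common odds ratio is the setting most favourable to a rank test, and that chi-square wins when the difference has no direction (step 6). The Biopsy question is directional, so the trade is reasonable, but it should be made knowingly.

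The Biopsy section also plans a biopsy at 12 months post-transplant as a baseline, which suggests comparing change. A Wilcoxon test at a single time point ignores baseline just as chi-square does. Proportional-odds regression can include a baseline grade taken before randomization. Since randomization may fall anywhere from 6 to 24 months, not every 12-month biopsy will qualify.

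A reader might infer something stronger: that the plan commits biopsy grades to the wrong test and so leaves the biopsy comparison short of power that it needs. The documents do not support this. They define no scale, and the power analysis is cited without inputs, so no shortfall can be shown.

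**Conclusion.** The point holds as one of efficiency. The only stated rule for discrete outcomes ignores order, CTCAE grades are ordered, and biopsy pathology may be. For a one-directional shift with an odds ratio of 2 to 2.5, a rank test gains roughly 14 to 16 percentage points at 46 versus 93, and about 10 to 17 points at 64 versus 128. For OR 2 in the CTCAE example the gain is about 19 points (85 − 66).

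These sizes rest on assumed grade distributions, a proportional-odds shift and a two-sided 5% level. They shrink to nothing for a binary outcome and reverse for a non-monotone one. Even the better test misses 44–47% of real effects at OR 2 with 46 versus 93, so the choice of test would not by itself make that comparison strong.

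Chi-square is valid here, and nothing is wrong with its error rate. The primary aim, the incidence of acute cellular rejection, is binary and unaffected. Priority is low: a worthwhile refinement of secondary and safety comparisons. The mismatch between 46 + 93 and 70% of 275 should be reconciled in any case.

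**What to change.** In Statistical Analysis, add wording to this effect: ordered outcomes (worst CTCAE grade per subject; biopsy pathology if graded) will be compared by Wilcoxon rank-sum or proportional-odds regression, with a common odds ratio and 95% CI from the latter; chi-square is kept for binary and unordered categories.

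Three definitions must go with it:

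- in Biopsy, the pathology endpoint, its scale and the time point of the main comparison;
- for CTCAE, one value per subject, with a stated category for subjects who have no event, so that several events in one subject are not counted as independent;
- which of the two methods gives the main p-value.

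The cost is a few sentences, with no added biopsies or subjects. The statistical price is lower power against a difference without direction, which a table of grade frequencies by arm would still show descriptively.

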### **Data Collection and Follow-up for Withdrawn Subjects**

Even though subjects may be withdrawn prematurely from the study, an attempt will be made to collect at least survival data on such subjects throughout the protocol defined follow-up period. Such data is important to the integrity of the final study analysis, since early withdrawal could possibly be related to the safety profile of the study. If a subject withdraws consent to participate in the study, attempts will be made to obtain permission to record at least survival data up to the protocol-described end of subject follow-up period.

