### **Stopping Rules**

Subjects diagnosed with two acute renal allograft rejection episodes post conversion from tacrolimus to sirolimus will be stopped from participating in the study and will be switched back to tacrolimus.

Subjects that develop significant side effects secondary to sirolimus (severe thrombocytopenia (platelets count <50, 000); severe hyperlipidemia not controlled by the use of statins or other cholesterol lowering agents; worsening proteinuria or severe de-novo proteinuria) will have sirolimus stopped and patients will be switched back to tacrolimus.

Subjects developing post-transplant infections (i.e., UTI, CMV, HSV, EBV, HCV, HBV, HIV, PCP), that in the opinion of the investigator are detrimental to the subject and their participation in this research trial, will be stopped from participating in this study.

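### Patient survival, graft survival, malignancy and infection are compared only by chi-square, which cannot handle early exit; if exits differ by arm, the bias can run either way

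*Combined protocol and SAP*

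**What the plan says.** The Statistical Analysis section is the whole analysis plan. It gives t tests for continuous variables, states that "chi square tests will be used to compare differences in discrete variables", and adds a logistic regression for factors "significantly associated with the development of acute rejection and renal allograft function after conversion from tacrolimus". That regression does not cover survival, malignancy or infection, and it makes no use of time.

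The Research Objective lists "patient and graft survival" as secondary aim ii, and the "incidence of hypertension, malignancies, and opportunistic infections and post-transplant DM" within aim iii. On duration, the Post randomization section says: "Both groups of patients will be followed for 4 years post-randomization".

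Early exit is part of the design:

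- **When and How to Withdraw Subjects** removes subjects in either arm for non-compliance, and for malignancy or infection that forces a change of immunosuppression.
- **Stopping Rules** adds that subjects with two rejections after conversion "will be stopped from participating in the study and will be switched back to tacrolimus". No matching rule exists for the tacrolimus arm.
- **Data Collection and Follow-up for Withdrawn Subjects** says that "an attempt will be made to collect at least survival data on such subjects" for the rest of the planned follow-up. Graft status, malignancy and infection are not named.
- **Adverse Event Reporting Period** closes 30 days after the last study treatment.

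The plan gives no censoring rule, analysis set or rule for subjects who leave early.

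**The concern.** A chi-square test needs a yes or no for each subject at a common time. For a subject who leaves at month 10 with a working graft, the 4-year answer is unknown unless someone finds out. The analyst must then either count that subject as event-free for the full 4 years or leave the subject out. The first choice lowers the observed event proportion in the arm with more exits. The second raises it, because event-free leavers fall out of the denominator while earlier events stay in.

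If the arms lose subjects at different rates, a difference in graft loss, malignancy or infection can therefore be produced, hidden or inflated by the handling alone. The two-rejection rule is a reason to expect unequal exits. The timing of events is discarded in every case.

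**Working it through.** **Inputs from the documents.** 4 years of follow-up; "we expect to be able to randomize 275 renal transplant patients into this protocol"; 2:1 allocation, so about 183 and 92. The Randomization section does not say which arm is larger. The planned biopsy counts (93 sirolimus, 46 tacrolimus) point to sirolimus. The documents give no event rate, exit rate, alpha or power for these outcomes, so there is no plan figure to reproduce.

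**Assumptions for illustration.** Constant hazard; 4-year risk R = 12% in both arms; exit proportion c = 35% (sirolimus) and 10% (tacrolimus); exits independent of events and uniform over either year 1 (U = 1) or all 4 years (U = 4).

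**Formulas.**

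- Hazard: λ = -ln(0.88)/4 = 0.0320 per year.
- Mean risk before exit: q = 1 - (1 - exp(-λU))/(λU), which is 0.0158 for U = 1 and 0.0613 for U = 4.
- Leavers counted as event-free: P = (1 - c)R + cq.
- Leavers dropped: P / [P + (1 - c)(1 - R)].

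Worked case (event-free, U = 1): sirolimus 0.65 × 0.12 + 0.35 × 0.0158 = 0.0835; tacrolimus 0.90 × 0.12 + 0.10 × 0.0158 = 0.1096.

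**No true difference (12% in both arms):**

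| Handling | Exits | Sirolimus | Tacrolimus | False difference (points) |
|---|---|---|---|---|
| Event-free | year 1 | 8.35% | 10.96% | -2.6 |
| Event-free | over 4 years | 9.94% | 11.41% | -1.5 |
| Dropped | year 1 | 12.74% | 12.15% | +0.6 |
| Dropped | over 4 years | 14.81% | 12.60% | +2.2 |

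With the same c in both arms the two proportions are identical and the false difference is zero under either handling.

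**True hazard ratio 1.5 against sirolimus.** The sirolimus risk is 1 - 0.88^1.5 = 17.4%, a true difference of 5.4 points. The same formulas, with λ multiplied by 1.5 for sirolimus (q = 0.0236 and 0.0900), give:

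| Handling | Exits in year 1 | Exits over 4 years |
|---|---|---|
| Event-free | 1.2 points | 3.1 points |
| Dropped | 6.3 points | 8.7 points |

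The same true harm can thus be shrunk to under a quarter or overstated by more than half.

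**Effect on the test.** Simulation of 1,000 trials per scenario: 92 tacrolimus and 183 sirolimus, two-sided 5% level, assumed tacrolimus risk 20%, exits 10% (tacrolimus) against 40% (sirolimus), exits independent of events. Simulation error is about 1 to 1.6 points. Rejection rates:

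| Truth | Exits | Chi-square, event-free | Chi-square, dropped | Log-rank |
|---|---|---|---|---|
| No difference | over 4 years | 10.5% | 11.4% | 5.1% |
| No difference | year 1 | 21.9% | 5.4% | 5.2% |
| Hazard ratio 1.5 | year 1 | 4.2% | 34.8% | 28.3% |

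Under no difference with year-1 exits, the Kaplan-Meier 4-year risks averaged 19.9% (sirolimus) and 20.0% (tacrolimus), against crude event-free proportions of 13.0% and 18.2%.

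**The case against.** The best defence has five parts.

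- **Patient survival is largely protected.** The plan tries to obtain survival data on withdrawn subjects through the full follow-up period, including those who withdraw consent, and says why this matters. Where vital status at 4 years is known, a fixed-time comparison of deaths is not biased by study exit; it loses only timing. This stands.
- **Unequal exit may be modest.** A reader might infer that every sirolimus stop is a study exit. The Stopping Rules do not say so: the side-effect rule switches the subject back to tacrolimus without stating that participation ends. Only the two-rejection rule is a study exit confined to sirolimus, and the Background reports no increased rejection risk after conversion in the team's retrospective series. The 35% against 10% is therefore an illustration, not a forecast. This stands.
- **Events that trigger withdrawal are already seen.** A malignancy or infection that causes exit has been observed, so only later or different events are lost. This stands. Later serious events judged possibly related are to be reported too, but that is not systematic ascertainment.
- **Survival methods are not a full cure.** Exit after two rejections is probably related to later graft loss, so censoring there is informative and Kaplan-Meier or Cox estimates would also be biased. This stands, and it is why the fix needs follow-up as well as a method.
- **These are secondary aims in a small trial.** With 92 against 183 subjects, power for 5% against 10% is about 27% at two-sided 0.05. This lowers the priority but does not justify a test that cannot use the data.

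None of this supplies a rule for leavers or a method that uses censored time.

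**Conclusion.** The concern holds and should be fixed. For four outcomes over 4 years, the only planned comparison ignores time and censoring, and the plan does not say how leavers are counted.

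A reader might infer that the arm with more exits will look safer. The documents do not support a fixed direction: that follows only if leavers are counted as event-free, and it reverses if they are dropped. Under the 12% risk and 35% against 10% exit assumptions, the false difference runs from -2.6 to +2.2 points depending on handling and exit timing, and it is zero with equal exits.

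Exposure is greatest for graft survival and for malignancy or infection occurring after exit. Patient survival is biased only to the extent that the promised survival follow-up fails. The primary rejection endpoint is not part of this point. Because the aims affected are secondary and the size rests on assumed exit rates, this is a should-fix matter.

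**What to change.** In the Statistical Analysis section:

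1. Analyse patient survival and graft survival from randomisation, by assigned arm, with Kaplan-Meier curves, a log-rank test and a Cox hazard ratio, censoring at last known status. State whether death with a working graft counts as graft loss.
2. Analyse malignancy and opportunistic infection by cumulative incidence, with death as a competing event.
3. Keep chi-square for outcomes known in every subject.

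In the section on follow-up of withdrawn subjects, extend the attempt at data collection to graft status, malignancy and infection through 4 years, since censoring alone does not deal with exits related to rejection. None of this changes a withdrawal or treatment rule.

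Cost: SAP wording, slightly more analysis work with standard software, dates of events and last contact on the case report form, and extra effort to trace subjects who leave. The tracing is the real cost, and it is easier to arrange while subjects are still in follow-up.
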